9.8.4. Data Safety Monitoring Board

An independent DSMB will be employed to review all available safety data for all patients at the time point when the last patient has completed 2 infusions at 30 mg/kg (approximately Week 8). This aggregate data review will be blinded unless the DSMB specifically requests unblinding at the patient or group level based on safety data summaries. The DSMB will be charged with advising the Sponsor about whether transitioning into the open-label extension period of the protocol is appropriate based on aggregate safety data from the double-blind dose-titration period. Based on the results of the DSMB review, the Sponsor will determine whether to roll over patients into the open-label extension period.

Any decision to interrupt, restart, or discontinue the study will be made by the Sponsor in consultation with the DSMB.

A formal DSMB meeting may be convened at any time if requested by the Sponsor of this study. The DSMB charter will provide further detail on the meeting and decision-making process involving the DSMB.

The outcome of any DSMB meeting will be communicated to the Investigators by the Sponsor. The relevant regulatory authorities will be promptly notified of study suspension or discontinuation related to safety concerns. Any suspension or discontinuation of the trial for any reason will also be promptly reported to the relevant Institutional Review Boards (IRB)/Independent Ethics Committee (IEC).

9.9. Randomization and Blinding

9.9.1. Randomization

After qualifying for study entry, DMD patients with a deletion confirmed as amenable to exon 45 skipping will be randomized using a 2:1 ratio to either SRP-4045 (8 patients) or placebo (4 patients). Randomization will be performed prior to dosing at Baseline/Week 1.

9.9.2. Blinding for Dose Administration

This study includes a double-blind, placebo-controlled dose-titration period of at least 12 weeks during which all patients, parents, Investigators, and site staff not involved with drug product preparation will be blinded to treatment assignment. A double-blind, placebo-controlled study

design will be used to reduce potential bias during data collection and evaluation of outcome parameters.

Eight patients will receive weekly IV doses of SRP-4045, and 4 patients will receive weekly IV doses of placebo in a blinded fashion until approximately 4 weeks after the last enrolled patient received 12 weeks of treatment. Only individuals (ie, the qualified pharmacist and back-up pharmacists) who are authorized to verify dose and dose assignment will be unblinded to treatment assignment. These individuals will not have interaction with study participants and will be instructed not to divulge randomization assignment to others under any circumstances, unless directed to do so by the Investigator in the interest of patient safety.

9.9.3. Unblinding Procedures

In the event of a medical emergency wherein the knowledge of the subject's treatment assignment may influence clinical decision-making, the Investigator has the option to unblind treatment assignment.

The reasons for any unblinding must be noted in the source documentation. The Investigator must not disclose information about treatment assignment to anyone who does not need the information due to their direct involvement in patient care.

If deemed necessary, the DSMB may request to review unblinded safety data for one or more patients at any time to ensure the safety of any individual patient or the study population as a whole. Data access will be restricted to DSMB members.

Regulatory authorities and/or the IRB/IEC may request the unblinding of one or more patients' data at any time.

9.10. Prior and Concomitant Medications and Therapeutic Procedures

The following therapies may be used prior to enrollment/randomization and throughout the study at the discretion of the Investigator. However, attempts should be made to keep the dosage constant throughout the treatment period, except to accommodate changes in weight.

- Oral corticosteroids for treatment of DMD including, but not limited to prednisolone and prednisone
- Oral ACE inhibitors including but not limited to perindopril and lisinopril
- Oral β -blockers including but not limited to carvedilol and atenolol
- Angiotensin-receptor blockers including but not limited to losartan, irbesartan, valsartan, and candesartan
- Oral laxatives including but not limited to lactulose, Senokot, and Movicol
- Vitamin D and calcium supplements
- Alendronate (Fosamax) or other bisphosphonates used to treat osteoporosis/osteopenia by inhibiting osteoclasts.
- Over-the-counter preparations such as herbal/non-herbal supplements, vitamins, minerals, and homeopathic preparations

Other concomitant medications (excluding other RNA-antisense or gene therapy agents) may also be taken, if, in the opinion of the investigator, they are not deemed to interfere with study procedures or the investigation of SRP-4045 in this study. Every attempt must be made to keep the dosage constant throughout the study period.

The following therapies are not permitted during the conduct of this study:

- Systemic or oral steroids for non-DMD conditions
- Investigational agents for the treatment of DMD
- Any medication with the potential to affect muscle mass, strength, and/or function, such as, but not limited to, growth hormone (hGH) and phosphodiesterase type 5 (PDE-5) inhibitors unless documented as medically necessary (eg, hGH prescribed by pediatric endocrinologist for treatment of short stature)
- Immunosuppressants (other than oral or systemic corticosteroids, as outlined)
- Systemic aminoglycoside antibiotics (unless discussed and agreed upon with the Investigator and the Medical Monitor)
- Statins (unless discussed and agreed upon with the Investigator and Medical Monitor)

9.11. Treatment Compliance

Treatment compliance with scheduled weekly infusions will be documented on the case report form (CRF).

10. STUDY ASSESSMENTS

Schedules of study events are provided in [Table 2](#) and [Table 3](#).

CCI

10.1. Screening Assessments

Written informed consent and assent will be obtained from the patient and/or parent as needed, by the Investigator or delegated study staff during the Screening period. The Investigator and study staff will also review all inclusion and exclusion criteria, medical history, medication history, physiotherapeutic intervention history, and documentation of DMD diagnosis during the Screening period.

In addition, at the Screening visit, all patients will undergo additional pre-treatment tests and procedures according to the timing on the schedules of events ([Table 2](#)). These tests and procedures are listed below.

- Whole blood for genotype/single nucleotide polymorphism (SNP)
- The 6MWT ([ATS 2002](#)) will only be performed at the screening visit to determine eligibility ([Table 2](#)). Patients will be asked to walk a set course of 25 meters for 6 minutes (timed) where the distance walked (in meters) will be recorded.
- Full physical examination (Section [10.3.2](#))
- Vital signs (Section [10.3.1](#)), as well as height and weight

CCI

- 12-lead ECG (Section [10.3.5.1](#))
- ECHO (Section [10.3.5.2](#))
- Blood and urine samples for clinical laboratory assessments (Section [10.3.3](#))

CCI

10.2. Baseline/Week 1 Assessments

The following Baseline/Week 1 assessments must be performed and results reviewed prior to randomization to confirm the patient is still eligible:

CCI

- Full physical examination (Section [10.3.2](#))

Once study eligibility has been confirmed at the Baseline/Week 1 visit, patients will be randomized (2:1) to blinded treatment with SRP-4045 or placebo. Patients will begin dosing at Baseline/Week 1 ([Table 2](#)).

Additional assessments to be performed at Baseline/Week 1 prior to dosing include:

- ECG (Section 10.3.5.1)

CCI

- Clinical laboratory assessments

CCI

- Pre-dose PK sample collection

Assessments to be performed at Baseline/Week 1 after dosing include:

- Plasma and urine collection for PK (Section 10.5)
- Post-infusion vital signs and observation period

Sampling for PK will be performed according to the procedures and times outlined in Section 10.5 and Table 2.

10.3. Safety Assessments

10.3.1. Vital Signs including Weight and Height

Vital signs including oral temperature, heart rate, respiratory rate and blood pressure as well as height and weight will be measured at the time points specified in the schedule of events (Table 2).

For infusion visits, vital signs are to be collected within approximately 30 minutes prior to the start of the infusion, and approximately 5, 30, and 60 minutes after the end of the infusion (ie, after investigational product has been flushed through the IV line). If the patient has not experienced an infusion reaction after 48 weeks of open-label treatment, collect vital signs prior to infusion and at 5 and 30 minutes post-infusion.

Vital signs will be performed after patients have remained seated for 5 minutes. Pulse rate and respiratory rate are to be measured over 1 minute.

Temperature is to be reported in degrees Celsius (°C).

Weight is to be reported in kilograms. If a patient's weight varies by more than 10% from the prior visit, the patient is to be re-weighed to confirm the result, and an explanation of the change must be documented.

Height is to be measured with shoes off. Ulna length should be collected measured when height is obtained for all patients. If standing height cannot be obtained, height is to be calculated using the following equation (Gauld 2004) for entry into the spirometry system:

$$\text{Height (cm)} = 4.605U + 1.308A + 28.003$$

where U is the length of the ulna in centimeters measured using an anthropometer or calipers, and A is the patient's age in years.

10.3.2. Physical Examination

Physical examinations will be performed by the Investigator or qualified study staff prior to dose administration according the schedule of events during the dose-titration and extension study period ([Table 2](#)) and the open-label introduction study period ([Table 3](#)). The assessments in [Table 3](#) will occur during the first 8 weeks of the open-label treatment period and are in addition to the assessments in [Table 2](#). Duplicate assessments at the same study visit should not be performed.

A full physical examination will include review of general appearance, head, eyes, ears, nose, and throat (HEENT), heart, lungs, abdomen, skin, lymph nodes, musculoskeletal, and neurological systems. A brief physical examination will include examination of general appearance, HEENT, heart, chest, abdomen, and skin.

10.3.3. Clinical Laboratory Assessments

All laboratory assessments, with the exception of PK sampling, must be performed prior to dose administration for all treatment visits.

Routine clinical laboratory testing will occur according the schedule of events during the dose-titration and extension study period ([Table 2](#)) and the open-label introduction study period ([Table 3](#)). The assessments in [Table 3](#) will occur during the first 8 weeks of the open-label treatment period and are in addition to the assessments in [Table 2](#). In the case of a duplicate assessment specified by [Table 2](#) and [Table 3](#) at the same study visit, only one assessment should be performed.

During Screening, safety laboratory assessments must be performed within 2 weeks prior to the Baseline/Week 1 visit, and results must be reviewed prior to dosing. If Screening safety laboratory samples were collected more than 2 weeks prior to the Baseline/Week 1 visit, samples must be collected again and results must be reviewed before patients may be dosed at Baseline/Week 1.

Before patients may begin dosing in the open-label extension period, safety laboratory assessments must be performed within 2 weeks prior to first dose, and the results of those labs reviewed prior to first dose. If safety laboratory samples were collected more than 2 weeks prior to the first open-label extension visit, samples must be collected again and results must be reviewed before dosing.

Laboratory results will be analyzed by an accredited central laboratory selected by the Sponsor (Sarepta Therapeutics). Assessments and shipment will be prepared according to the Laboratory Manual provided for the study. Specific laboratory parameters to be analyzed are presented in the subsections below.

10.3.3.1. Hematology

Hematology parameters to be analyzed include the following:

Red blood cells (RBC)	Lymphocytes
White blood cells (WBC)	Monocytes
Hemoglobin	Eosinophils
Hematocrit	Basophils
Neutrophils	Platelets

10.3.3.2. Coagulation

Coagulation parameters to be analyzed include the following:

Prothrombin time	International Normalized Ratio (INR)
Activated partial thromboplastin time (aPTT)	

10.3.3.3. Serum Chemistry

Serum chemistry parameters to be analyzed include the following:

Sodium	Alkaline phosphatase
Chloride	Amylase
Potassium	Alanine aminotransferase (ALT)
Calcium	Aspartate aminotransferase (AST),
Glucose	Gamma-glutamyl transferase (GGT)
Creatinine	Lactate dehydrogenase (LDH)
Blood urea nitrogen (BUN)	C-reactive protein (CRP)
Albumin	Creatine kinase (CK)
Uric acid	Total bilirubin
Cystatin C	

10.3.3.4. Urinalysis

The following parameters will be analyzed:

pH	Urine microscopy
Specific gravity	Hemoglobin
Protein	Kidney injury molecule-1 (KIM-1)
Glucose	Ketones

Any laboratory value(s) outside of the current reference range will be flagged.

10.3.4. Concomitant Medications and Physiotherapeutic Intervention

Concomitant medications, changes in dosage of concomitant medications, and concomitant therapies will be reviewed and recorded at each visit ([Table 2](#)) from the time the parent(s)/guardian(s) sign(s) the informed consent and the patient signs the assent form (if applicable). Information on any physiotherapeutic intervention must be collected in detail for this study.

10.3.5. Other Safety Assessments

10.3.5.1. Electrocardiogram (ECG)

A 12-lead ECG will be performed at the time points specified in the schedule of events for the dose-titration and extension study period ([Table 2](#)) and the open-label introduction study period ([Table 3](#)). The assessments in [Table 3](#) will occur during the first 8 weeks of the open-label treatment period and are in addition to the assessments in [Table 2](#). Duplicate assessments at the same study visit should not be performed.

ECGs are to be performed at a consistent time of day throughout the study. ECGs will be performed only after the patient is positioned supine, resting, and is quiet for a minimum of 15 minutes. The ECG will be manually reviewed and interpreted by medically qualified personnel using a central vendor according to pre-specified criteria. The Investigator will review the results of the centrally read ECG report and determine if abnormal findings are clinically significant.

[figure not shown]
10.3.5.2. Echocardiography (ECHO)

A standard 2-dimensional (2D) ECHO will be performed at the time points specified in the schedule of events ([Table 2](#)). ECHOs will be performed at a consistent time of day throughout the study. The ECHO will be reviewed and interpreted by medically qualified personnel using a central vendor according to pre-specified criteria. Ejection fraction (EF) will be noted. The Investigator will review the results of the ECHO report and determine if abnormal findings are clinically significant.

[figure not shown]
10.3.5.3. Adverse Events

The collection of AEs is described in Section [11](#).

[figure not shown]
CCI

CCI

CCI

10.5. Pharmacokinetic Assessments

10.5.1. Blood Sample Collection

Blood collection for serial PK determination will occur at the time points specified in the schedule of events (Table 2): immediately pre-infusion, at approximately 5 to 10 minutes after the end of infusion, and then at approximately 1, 1.5, 2, 4, 6, 8, 12, 16, and 24 hours after the end of infusion at Baseline/Week 1 and Weeks 3, 5, 7, and 60.

CCI

Blood collection for PK must be drawn from the arm contralateral to the treatment infusion. Pharmacokinetic samples may not be drawn from a patient's implanted venous port if treatment is infused via the port.

10.5.2. Urine Sample Collection

Urine for PK determination will be collected on a cumulative basis, during the following time intervals at the time points specified in the schedule of events (Table 2) based on start time of study drug infusion: 0 to 4 hours, 4 to 8 hours, 8 to 12 hours, 12 to 24 hours, and additionally at Week 7, 24-36 hours. Patients will be asked to void their bladder prior to start of study drug infusion.

11. ADVERSE EVENTS

11.1. Collection of Adverse Events

All AEs from the time of informed consent through the end of study visit (or early termination from the study) will be recorded in each individual patient's electronic case report form (eCRF). For patients who prematurely discontinue from the study (see Section 8.3), AEs will continue to be recorded until 4 weeks after the last infusion. Over the entire duration of the study, site personnel will ensure that all AEs are recorded appropriately. If an AE occurs, the primary concern is for patient safety and the investigator will use his/her judgment and expertise to determine the appropriate course of action.

If, at any time after the patient has completed participation in the study (see Section 8.3), the Investigator or study staff becomes aware of an SAE that the Investigator believes is possibly/probably or definitely related to the investigational drug product (Section 11.3.1) or is possibly/probably or definitely related to a study procedure (Section 11.3.2), then the event and any known details must be reported promptly to the Sponsor.

11.2. Definition of Adverse Events

11.2.1. Adverse Event (AE)

An AE is any untoward medical occurrence in a clinical trial participant, which does not necessarily have a causal relationship with the investigational drug. An AE can, therefore, be any unfavorable and unintended symptom, sign, disease, condition, or test abnormality that occurs during or after administration of an investigational drug product whether or not considered related to the investigational drug product. Adverse events include:

- Symptoms described by the patient or signs observed by the Investigator or medical staff.
- Test abnormalities (laboratory tests, ECG, X-rays, etc) that result in an alteration in medical care (diagnostic or therapeutic).

Abnormalities present at Screening are considered Medical History. These abnormalities will be considered AEs only if they reoccur after resolution or worsen after signing consent.

11.2.2. Serious Adverse Event (SAE)

An SAE is defined as any AE that results in any of the following:

Death: The patient died as the result of the event.

Life-threatening event: Any AE that places the patient, in the view of the Investigator or Sponsor, at immediate risk of death from the AE as it occurred, ie, does not include an AE that had it occurred in a more severe form, might have caused death.

Required or prolonged inpatient hospitalization: The AE resulted in hospitalization or prolonged an existing hospitalization. Since hospitalization may be part of the study, only hospitalizations that are longer than expected based on Investigator judgment, will be considered prolonged hospitalizations.

Persistent or significant disability/incapacity: An AE that results in a substantial disruption of a person's ability to conduct normal life functions.

Congenital anomaly/birth defect: A congenital anomaly/birth defect that occurs in the offspring of a patient exposed to the investigational product.

Important medical events: An AE that may not result in death, be life-threatening, or require hospitalization may be considered an SAE when, based upon appropriate medical judgment, the event may jeopardize the patient and may require medical or surgical intervention to prevent one of the outcomes listed above.

11.3. Classification of Adverse Events

Each AE whether serious or non-serious will be classified by the Investigator according to the following rules and definitions.

11.3.1. Relationship to Investigational Drug Product

For each AE the Investigator determines whether there is a reasonable likelihood that the AE may have been caused by the study treatment according to the categories below:

Unrelated: The event is clearly not related to the investigational drug product

Possibly/Probably Related: The event could be related/is likely to be related to the investigational drug product

Definitely Related: The event is clearly related to the investigational drug product

Adverse events that the Investigator or Sponsor considers to be possibly/probably or definitely related to the investigational drug product will be considered adverse drug reactions.

11.3.2. Relationship to Study Procedures

For each AE the Investigator determines whether there is a reasonable possibility that the AE may have been caused by the study procedures according to the categories below:

Unrelated: The event is clearly not related to study procedures

Possibly/Probably Related: The event could be related/is likely to be related to study procedures

Definitely Related: The event is clearly related to study procedures

11.3.3. Relationship to Underlying Disease

For each AE the Investigator determines whether there is a reasonable possibility that the AE may be related to the underlying disease according to the categories below:

Unrelated: The event is clearly not related to underlying disease

Possibly/Probably Related: The event could be related/is likely to be related to underlying disease

Definitely Related: The event is clearly related to underlying disease

Adverse events of disease progression may be considered AEs, based on the investigator's discretion.

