7.3. Study Endpoints

The following study endpoints will be evaluated in this study. Descriptions of all study assessments and procedures are provided in Section 10.

The primary endpoint is assessment of the safety of SRP-4045 during the double-blind dose-titration period according to the following:

- Incidence of AEs

- Incidence of clinical laboratory abnormalities (hematology, chemistry, coagulation, urinalysis)
- Incidence of abnormalities in vital signs and physical examinations
- Clinically significant worsening of ECGs and ECHO

The secondary endpoint is to determine the PK profile of SRP-4045 during the double-blind dose-titration period:

[figure not shown]
- Maximum plasma concentration (C_{max})
- Time to maximum plasma concentration (T_{max})
- Area under the plasma concentration-curve (AUC)
- Apparent volume of distribution at steady state (V_{ss})
- Elimination half-life ($t_{1/2}$)
- Total clearance (CL)
- Mean residence time (MRT)
- Urinary clearance (CL_R)

CCI

[figure not shown]

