#### **6.8.3. Additional AE for Review**

Additional TEAEs for review will be summarized by SOC and PT for each Analysis Period and treatment group as defined in Section 5.1 and by dose level for the double-blind period summary. All standard MedDRA queries ([SMQs] based on MedDRA Version 17.1) listed below will include broad and narrow terms. The AEs for additional review are:

- •infusion site reaction (extravasation events SMQ and the following PTs: application site erythema, application site rash, catheter site hematoma, catheter site hemorrhage, catheter site-related reaction, infusion site rash, infusion site swelling)
- •leukopenia and neutropenia (haematopoietic leukopenia SMQ)
- •severe cutaneous adverse reactions (severe cutaneous adverse reactions SMQ)
- •drug-induced hepatotoxicities (cholestasis and jaundice of hepatic origin SMQ, hepatic failure, fibrosis, cirrhosis and other liver damage-related conditions SMQ, hepatitis, non-infectious SMQ, liver neoplasms, benign [including cysts and polyps] SMQ, liver malignant tumors SMQ, liver tumors of unspecified malignancy SMQ, liver related investigations, signs and symptoms SMQ, liver-related coagulation and bleeding disturbances SMQ)
- •cardiac events (cardiomyopathy SMQ, cardiac failure SMQ, and arrhythmia related investigations, sign and symptoms SMQ)
- •coagulopathy (haemorrhage terms [excluding lab terms] SMQ, haematopoietic thrombocytopenia SMQ, PTs in the embolism and thrombosis High Level Group Terms [HLGT])

An overall summary of additional AE for review will include total number of events, number of serious events, number of treatment-related events, number of unrelated events, number of mild events, number of moderate events, number of severe events, and number of events occurring on the same day as an infusion (within 24 hours or on the same day with no time).

A listing of each AE for additional review strategy and a listing of AEs related to study drug for each AE for additional review strategy will be generated.

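### Protocol 11.3.3 lets each investigator decide whether a disease-progression event is recorded as an adverse event, which contradicts 11.1, 11.2.1 and 11.4

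*Protocol*

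**What the plan says.** Protocol 11.3.3 asks the investigator to rate each AE's relationship to the underlying disease on three levels, then adds: "Adverse events of disease progression may be considered AEs, based on the investigator's discretion". The visible text gives no definition of progression, no criteria for the choice and no central check on it.

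The recording rules elsewhere have no such exception:

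- Protocol 11.2.1: "An AE is any untoward medical occurrence in a clinical trial participant, which does not necessarily have a causal relationship with the investigational drug". On abnormalities already present at Screening: "These abnormalities will be considered AEs only if they reoccur after resolution or worsen after signing consent".
- Protocol 11.1 requires "All AEs from the time of informed consent through the end of study visit" to go into the eCRF. Section 11.4 repeats the duty up to 4 weeks after the last dose and includes relationship to underlying disease among the items recorded.

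Drug causality is rated only after an event has been called an AE (Protocol 11.3.1): "For each AE the Investigator determines whether there is a reasonable likelihood that the AE may have been caused by the study treatment".

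In Protocol 7.3 the primary endpoint covers the double-blind period and has four components. "Incidence of AEs" is the one listed first; "Clinically significant worsening of ECGs and ECHO" is the last.

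SAP 6.8.1 tabulates TEAEs by severity and by relationship to study drug, but plans no table by relationship to underlying disease. The events of special interest in SAP 6.8.2 and the additional events in 6.8.3 are summarised from TEAEs. The latter include a cardiac group built from "cardiomyopathy SMQ, cardiac failure SMQ" and arrhythmia terms.

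**The concern.** Attribution to disease is used here as an entry filter, although the same section already collects it as a data field. Two sites can both comply with the protocol and treat the same event differently. The filter also acts before the drug-causality question is asked, so an event set aside as progression is never rated against SRP-4045.

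This matters in a first-in-human study of patients with advanced DMD. Drug-caused worsening that resembles the disease is the kind of event such a filter is most likely to remove, and AE incidence is one of the primary safety measures.

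**Working it through.** The plan states no event rate, power or other figure on this point, so there is nothing to reproduce. The check is a comparison of texts, then a tracing of consequences, then simple arithmetic on size.

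**1. Do the sections conflict?** Under 11.2.1 a symptom or sign that worsens after consent is an AE whatever its cause, and 11.1 and 11.4 require all AEs to be recorded. Under 11.3.3 the same event may or may not be one. The sentence in 11.3.3 is circular, since it already calls the events adverse events. It can be read as permitting entry or as excusing omission. Either reading leaves the choice to the investigator, and nothing visible in the Protocol or SAP settles it.

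**2. What does an omitted event miss?**
- The causality rating in 11.3.1.
- The AE-incidence component of the primary endpoint.
- Two of the six stopping criteria in Protocol 9.8.3: the count of related severe or moderate AEs, and any related SAE.
- The SAP 6.8.2 and 6.8.3 event summaries.

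**3. What is captured anyway?**
- Three of the four primary components: laboratory abnormalities, vital signs and examinations, and ECG/ECHO worsening. Laboratory tests go to a central laboratory (10.3.3), and ECG and ECHO are read centrally (10.3.5.1, 10.3.5.2).
- Cardiac decline seen on ECHO. SAP 6.8.6 with Appendix Table 5 tabulates LVEF below 55% and fractional shortening below 29%, independently of AE coding.
- The other four stopping criteria, which are laboratory values.
- Deaths (11.6.2). Other serious events are largely protected because 11.5 triggers reporting when an event meets a seriousness criterion, with no exemption for progression. The protection is not complete, since 11.2.2 defines an SAE as a kind of AE.

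The gap is therefore mainly non-serious clinical worsening.

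**4. Size for one patient.** Inputs: 8 active and 4 placebo (Protocol 7.1).
- Single preferred term, active: 1/8 = 12.5 points.
- Single preferred term, placebo: 1/4 = 25 points.
- Any TEAE: 0 points if the patient has another recorded TEAE, because SAP 6.8.1 counts patients.

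**5. Under-counting (illustrative).** Let p be the true risk of an event type and q the chance that it is recorded; both are assumed. The chance of at least one recorded case among 8 active patients is 1 − (1 − pq)^8.

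| p | q = 1 | q = 0.5 |
|---|---|---|
| 0.10 | 57.0% | 33.7% |
| 0.20 | 83.2% | 57.0% |
| 0.30 | 94.2% | 72.8% |

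**6. Site imbalance (extreme case).** Assume four equal sites (12/4 = 3 patients each), no stratification by site (none is described), the same progression event in all 12 patients, and one site that records none. The chance that this site holds k placebo patients is C(4,k)·C(8,3−k)/C(12,3), with C(12,3) = 220. The recorded difference, active minus placebo, is (5+k)/8 − (4−k)/4.

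| k | Probability | Difference (points) |
|---|---|---|
| 0 | 56/220 = 25.5% | −37.5 |
| 1 | 112/220 = 50.9% | 0 |
| 2 | 48/220 = 21.8% | +37.5 |
| 3 | 4/220 = 1.8% | +75 |

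A spurious difference of at least 37.5 points in either direction has probability (56 + 48 + 4)/220 = 49.1%. The average difference is (−37.5×56 + 37.5×48 + 75×4)/220 = (−2100 + 1800 + 300)/220 = 0. Site habit adds chance imbalance, but by itself it does not favour an arm.

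**The case against.** The strongest reply is that this is a loose sentence with little reach. Most safety information is collected on schedule whatever the investigator calls an AE. The toxicity the protocol expects is renal (9.8.1) and is followed by laboratory markers. Inclusion criterion 3 selects patients whose cardiac and pulmonary function is judged unlikely to decompensate. An investigator convinced that an event is progression may also rate it unrelated to drug once it is recorded, so the remedy restores visibility only in part. SAP 4.5.1 describes periodic safety reviews in the past tense, which suggests that the study was well under way and that past omissions cannot be recovered by new wording.

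Much of this stands, and it rules out several stronger readings that a reader might infer:

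- *The whole primary endpoint depends on site habit.* Only one of its four components does.
- *A fall in cardiac function would be missing at some sites.* A fall seen on a scheduled ECHO is measured and tabulated at every site; it could only be missing as an AE. Whether respiratory measures give the same backstop cannot be judged, because parts of the assessments are blacked out.
- *The placebo comparison is biased towards the drug.* Investigators are blinded in the period that the primary endpoint covers (9.9.2). The choice is made knowing that the patient is on drug only in the open-label period, which lies outside that endpoint.
- *One site could take 25 points (3/12) off AE incidence.* That needs equal sites, a progression event in all three patients at one site and no other TEAE in any of them. It also pools the arms.

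The reply does not remove the conflict between the sections or the loss of a causality rating for an omitted event. Scheduled data carry no such rating and do not enter the AE tables.

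**Conclusion.** The point holds in limited form. Section 11.3.3 contradicts 11.1, 11.2.1 and 11.4, and no visible text reconciles them. The consequence is that non-serious clinical worsening may go unrecorded as an AE, without a drug-causality rating, depending on the site.

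In the double-blind period the expected effect is under-counting and chance site imbalance. In the open-label period the same discretion is exercised with treatment known, so its AE counts deserve more caution. The size that follows from the design alone is 12.5 or 25 points per omitted patient on a single preferred-term row, and possibly nothing on any-TEAE incidence. The recording probabilities and the site scenario rest on assumed inputs, and the latter is an extreme case; neither is a forecast. The inconsistency should be corrected, but it does not undermine the primary endpoint as a whole.

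**What to change.** In Protocol 11.3.3, replace the discretionary sentence with a statement that progression events meeting the 11.2.1 definition are recorded as AEs, with their relationship to investigational drug and to underlying disease both rated.

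In SAP 6.8.1, add a table of TEAEs by relationship to underlying disease, so that readers can see incidence with and without events judged disease-related. The field is already among the items recorded under Protocol 11.4. Add a note that events before the change were recorded under the discretionary rule.

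The cost is one sentence, one table, more AE entries and higher crude AE percentages, which the new table would explain. If the change is made mid-study, the dataset contains two recording rules and only later events benefit. The table and the note can still be added before the final analysis.
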